9. PATIENT ASSESSMENTS AND TOXICITY

Assessment	Pre-entry		Follow-up (# of months from last radiation therapy treatment)									
			1	3	6	12	18	24	30	36	48	60
History	X			X	X	X	X	X	X	X	X	X
Physical exam (DRE)	X			X	X	X	X	X	X	X	X	X
ECOG Performance Scale	X			X	X	X	X	X	X	X	X	X
Prostate Biopsy & Gleason score	X											
PSA	X			X	X	X	X	X	X	X	X	X
Prostate volume assessment	X											
CBC, platelets	X											
BUN, creatinine	X											
Toxicity evaluation	X			X	X	X	X	X	X	X	X	X
AUA score	X			X	X	X	X	X	X	X	X	X
EPIC-26 Questionnaire	X			X	X	X	X	X	X	X	X	X
SHIM Questionnaire	X			X	X	X	X	X	X	X	X	X

Follow up evaluations may be performed +/- 30 days

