2. OBJECTIVES

PRIMARY OBJECTIVES:

- Document the efficacy of the CyberKnife® procedure, where efficacy is defined by biochemical Disease-Free Survival (bDFS), using Phoenix and ASTRO definitions, at 5 years.

- Compare the CyberKnife® Stereotactic Radiosurgery System bDFS rate to published HDR monotherapy bDFS rates reported in the literature.

SECONDARY OBJECTIVES:

- Measure rates of acute and late grade 3-5 gastrointestinal and genitourinary toxicity observed during the five years following CyberKnife® Stereotactic Radiosurgery System for prostate cancer. Acute toxicity will be defined as occurring within 90 days from completion of treatment. Late toxicity will be defined as occurring more than 90 days from completion of treatment. It is graded based upon Common Terminology Criteria for Adverse Events (CTCAE), v3.0 and RTOG/ECOG definitions (see appendix 5).
- Measure rates of local failure, distant failure, clinical disease-free survival, disease-specific survival, and overall survival
- Examine Quality of Life (QOL) in generic and organ-specific domains

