9.1. EVALUATION DURING TREATMENT & FOLLOWING TREATMENT

9.1.1. PRE-ENTRY ASSESSMENT: see section 4.7.

9.1.2. Stereotactic radiosurgery is an outpatient procedure. Patient management immediately after the procedure will follow routine patient care guidelines as determined by the physician. Subjects will be provided instructions on who to call with specific contact information, in the event they experience any untoward effects following treatment. In the event a subject experiences any untoward effects following CyberKnife® treatment, information specific to the patient's condition and symptoms, treatment intervention required, and hospital stay and course will be recorded for purposes of clinical evaluation.

9.1.3. ASSESSMENTS FOLLOWING TREATMENT: At 1 month following last radiation treatment, patients will be assessed for

acute toxicity, and will fill out AUA form, EPIC-26 and SHIM. At month 3, every 6 months from year 1-3 (months 6, 12, 18 and 24, 30 and 36) and at year 4 and 5, AUA, EPIC-26 and SHIM will be administered, and an H&P with DRE and toxicity evaluation will be completed. Examination and studies may be done at outside facility.

9.1.4. Recommended: at the time of biochemical failure, or when the patient develops signs of symptoms suggesting metastatic disease, it is at the physician's discretion to perform a prostate biopsy or imaging studies.

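### The ±30-day visit tolerance equals the whole interval at month 1, so month-1 scores can be taken anywhere from about day 0 to day 60 and can describe non-overlapping periods

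*Combined protocol and SAP*

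**What the plan says.** The section 9 table counts follow-up in months from the last radiation treatment, with visits at months 1, 3, 6 and onward to 60. Its footnote reads "Follow up evaluations may be performed +/- 30 days". Neither the table nor section 9.1 gives a tighter tolerance for any visit.

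Section 9.1.3 sets the content of the early visits. For the visit one month after radiation ends, the text lists "acute toxicity, and will fill out AUA form, EPIC-26 and SHIM". From the third month onward the same questionnaires are given and "an H&P with DRE and toxicity evaluation will be completed".

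Section 2 makes acute and late grade 3-5 gastrointestinal and genitourinary toxicity a secondary objective and sets the boundary: "Acute toxicity will be defined as occurring within 90 days from completion of treatment", and "Late toxicity will be defined as occurring more than 90 days from completion of treatment". Quality of life is also a secondary objective. Section 11.1 says that toxicity and quality of life will be reported descriptively.

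Section 9.1.2 adds a route that does not depend on visits. "In the event a subject experiences any untoward effects following CyberKnife® treatment", details of the symptoms, the intervention and any hospital course are to be recorded.

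**The concern.** A 30-day tolerance is small beside a 12-month interval, but it is 100% of a 1-month interval. Symptoms can change a good deal in the first two months after radiation, and the month-1 visit is the one meant to describe that time. If it can take place on the last day of treatment or two months later, the month-1 summary mixes men at different points of recovery. Some of their answers may refer mainly to time before or during treatment.

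Two secondary objectives are touched: early quality of life, and acute toxicity so far as it depends on scheduled evaluations.

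**Working it through.** **Inputs**
- Tolerance: ±30 days for all visits (section 9 footnote).
- Day 0: last radiation treatment (section 9 table header).
- Acute period: days 0 to 90 (section 2).
- Recall periods (Appendix VI): last 4 weeks for most EPIC-26 items, about the past month for the AUA index, 6 months for SHIM.
- Duration of the CyberKnife course: under 10 days in section 8.4.4.1, within 7 days in section 8.5.3. These limits differ and should be reconciled; both are carried through below.
- Assumption: 1 month = 30 days, with 28 to 31 days as a range.

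**Step 1. Permitted visit days.** Window = nominal day ± 30.
- Month 1: 30 ± 30 = days 0 to 60.
- Month 3: 90 ± 30 = days 60 to 120.
- With months of 28 to 31 days, the month-1 window starts between day -2 and day 1 and ends between day 58 and day 61. The month-3 window starts between day 54 and day 63 and ends between day 114 and day 123. The month convention hardly matters at month 1.

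**Step 2. EPIC-26 recall.** A form completed on day d covers days d - 28 to d. Two forms do not overlap when their dates differ by more than 28 days.
- Day 0 covers days -28 to 0; day 60 covers days 32 to 60. No overlap.
- At half the tolerance, day 15 covers days -13 to 15 and day 45 covers days 17 to 45. Still no overlap.

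**Step 3. Pre-treatment share of a day-0 form, monotherapy.**
- Course under 10 days: at least (28 - 10)/28 = 18/28 = 64%.
- Course within 7 days: at least (28 - 7)/28 = 21/28 = 75%.

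Boost patients also receive IMRT, and visits count from the last radiation of either kind. The documents do not state how long IMRT takes, so no such share can be computed for them.

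**Step 4. Scheduled toxicity evaluations in the acute period.** The month-3 window contains 61 permitted days. Days 60 to 90 (31 days) are in the acute period and days 91 to 120 (30 days) are after it.
- Month 3 by day 90: there are two scheduled evaluations in the acute period, whenever month 1 took place.
- Month 3 after day 90: month 1 is the only one.
- Month 1 on day 0 and month 3 after day 90: the only scheduled evaluation in the acute period is on day 0.

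At the other extreme, both visits could be made at about day 60.

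**The case against.** The day-0 case needs two extremes together: month 1 on its earliest permitted day and month 3 in the later half of its window. The nominal target is still 1 month, and most visits will probably fall nearer to it. This is right. A reader might infer that the month-1 window alone leaves acute toxicity assessed only on day 0, and the documents do not support that.

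A reader might also infer that acute events between visits rest on recall alone. Section 9.1.2 says otherwise: patients are told whom to call, and untoward effects are recorded with their treatment and hospital course. The stated endpoint is grade 3-5 toxicity, the kind most likely to lead to contact. This too stands. It protects milder toxicity less well, and it does nothing for questionnaire scores.

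Nor does a month-3 visit that straddles day 90 misclassify events. Section 2 already separates acute from late by time of occurrence, so no new classification rule is needed. The case report forms are not reproduced, so nothing can be said about whether they record onset dates.

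The gap of about 120 days from day 0 to day 120 might be taken as the longest between any two assessments. It is the maximum only between months 1 and 3. Month 3 on day 60 and month 6 on day 180 + 30 = 210 are 150 days apart, and later intervals are longer still.

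Finally, section 11.1 plans no test or comparison at month 1, and SHIM, with its 6-month recall, is much less sensitive to a 30-day shift. Both points limit the consequences. Neither removes the mixing of periods in the EPIC-26 and AUA scores.

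**Conclusion.** The concern holds as a minor design weakness. One tolerance for all visits lets month 1 fall anywhere from about day 0 to day 60, and EPIC-26 forms completed more than 28 days apart within that window share no recall period. For monotherapy, a day-0 form is at least 64% pre-treatment under the 10-day limit, or 75% under the 7-day limit. For scheduled toxicity evaluation, the worst compliant case leaves day 0 as the only one in the acute period, but only with month 3 after day 90 and with event-driven recording still in place.

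The conclusion assumes months of 28 to 31 days and summaries by nominal visit; section 11.1 gives no rule that uses the actual date. The 64% and 75% figures apply only to monotherapy patients seen on day 0. The documents do not show how visit dates will in fact be spread, so no bias in a reported rate or score can be estimated.

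**What to change.** Change the footnote to the section 9 table so that the early visits have narrower windows, for example ±7 days at month 1 and ±14 days at month 3, and keep ±30 days from month 6. The exact widths are a matter of judgement and clinic logistics.

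With these values month 1 falls on days 23 to 37. The largest separation is 14 days, so any two EPIC-26 recall periods share at least 28 - 14 = 14 days. The earliest form reaches back only 28 - 23 = 5 days before the last treatment. Month 3 falls on days 76 to 104 and still straddles day 90, so a man may still have just one scheduled evaluation in the acute period. It would then be no earlier than day 23.

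The cost is one edited footnote and a few more early visits counted as out of window.

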9.1. EVALUATION DURING TREATMENT & FOLLOWING TREATMENT

9.1.1. PRE-ENTRY ASSESSMENT: see section 4.7.

9.1.2. Stereotactic radiosurgery is an outpatient procedure. Patient management immediately after the procedure will follow routine patient care guidelines as determined by the physician. Subjects will be provided instructions on who to call with specific contact information, in the event they experience any untoward effects following treatment. In the event a subject experiences any untoward effects following CyberKnife® treatment, information specific to the patient's condition and symptoms, treatment intervention required, and hospital stay and course will be recorded for purposes of clinical evaluation.

9.1.3. ASSESSMENTS FOLLOWING TREATMENT: At 1 month following last radiation treatment, patients will be assessed for

acute toxicity, and will fill out AUA form, EPIC-26 and SHIM. At month 3, every 6 months from year 1-3 (months 6, 12, 18 and 24, 30 and 36) and at year 4 and 5, AUA, EPIC-26 and SHIM will be administered, and an H&P with DRE and toxicity evaluation will be completed. Examination and studies may be done at outside facility.

9.1.4. Recommended: at the time of biochemical failure, or when the patient develops signs of symptoms suggesting metastatic disease, it is at the physician's discretion to perform a prostate biopsy or imaging studies.

9.2. CRITERIA FOR TOXICITY

9.2.1. ACUTE AND LATE TOXICITY

9.2.2. Side effects will be assessed using the NCI Common Toxicity Criteria version 3.0 (see appendix V).

9.3. QUALITY OF LIFE ASSESSMENTS

9.3.1. EXPANDED PROSTATE CANCER INDEX COMPOSITE

(EPIC)-26: is a validated comprehensive instrument developed to assess patient function and bother after prostate cancer treatment. It was developed by an expert panel of urological oncologists, radiation oncologists (including those with brachytherapy expertise), survey researchers, and prostate cancer nurses, to address symptoms related to radical prostatectomy, external beam radiotherapy, prostate brachytherapy, and hormonal symptoms. See appendix VI.

9.3.2. AMERICAN UROLOGICAL ASSOCIATION (AUA) SYMPTOM INDEX:

Also known as the International Prostate Symptom Score (IPSS), this widely used index assesses urinary symptom bother. See appendix VI.

9.3.3. SEXUAL HEALTH INVENTORY FOR MEN (SHIM):

is a widely used, internationally validated and sensitive instrument for assessing erectile dysfunctionⁱ.

9.4. CRITERIA FOR DISEASE CONTROL: intervals will be measured from enrollment date.

9.4.1. BIOCHEMICAL DISEASE-FREE SURVIVAL (bDFS):

is measured as time to PSA failure. While earlier reports of prostate cancer patients treated with radiotherapy have used the ASTRO consensus definition (ACD) of PSA failure, recent studies^{ii, iii, iv} have suggested the “nadir+2” definition is a more sensitive and specific definition of biochemical failure. Indeed, a recent expert panel met in Phoenix^v and developed a consensus recommendation using the latter definition. So that comparisons can be made with earlier literature, both definitions shall be used:

9.4.1.1. Phoenix definition:

failure occurs when the PSA is ≥ 2 ng/ml more than the lowest PSA measurement before the current one, with no backdating. Administration of salvage therapy (hormones, surgery, etc...) will be considered failure.

9.4.1.2. Strict ASTRO Consensus Definition (ACD):

failure is defined as three consecutive rises in post-treatment PSA, measured at the specified follow-up intervals. If three consecutive PSA rises occur during the

first 2 years after treatment, followed by a non-hormonal induced PSA decline, this will not be considered a failure. Administration of salvage therapy (hormones, surgery, etc...) will be considered failure. Failure date is the midpoint between the dates of the last non-rising PSA and the first PSA rise.

9.4.2. CRITERIA FOR LOCAL FAILURE:

Clinical evidence of local progression or recurrence: Clinical failure includes a palpable abnormality that has increased in size, failure of regression of a palpable abnormality by 2 years after treatment, or redevelopment of a prostate abnormality after complete response. Patients with a prostate abnormality compatible with local recurrence or a PSA failure shall undergo a prostate biopsy. A histologic criterion for local failure is a positive prostate biopsy more than 2 years after treatment. Patients with a normal exam and no evidence of PSA failure shall be considered controlled locally. Patients with clinical failure and no biopsy are considered local failures. If a patient is locally controlled at the time of orchiectomy or androgen ablation, he is censored and considered “not evaluable” for further local control.

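### Dated from enrollment, a 5-year Kaplan-Meier bDFS misses nearly all Phoenix failures first found at the 60-month visit, and the ASTRO rate captures first rises only to month 36

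*Combined protocol and SAP*

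**What the plan says.** The primary objective (Section 2) is bDFS at 5 years by both the Phoenix and ASTRO definitions, with a comparison against published HDR monotherapy rates.

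- **Time origin (9.4):** "CRITERIA FOR DISEASE CONTROL: intervals will be measured from enrollment date".
- **Visit clock (Section 9 table):** "Follow-up (# of months from last radiation therapy treatment", with PSA at months 3, 6, 12, 18, 24, 30, 36, 48 and 60, and "Follow up evaluations may be performed +/- 30 days". Section 9.1.3 labels the last two visits by year: "and at year 4 and 5, AUA, EPIC-26 and SHIM will be administered".
- **Phoenix (9.4.1.1):** "failure occurs when the PSA is ≥ 2 ng/ml more than the lowest PSA measurement before the current one, with no backdating".
- **ASTRO (9.4.1.2):** "failure is defined as three consecutive rises in post-treatment PSA, measured at the specified follow-up intervals". On dating: "Failure date is the midpoint between the dates of the last non-rising PSA and the first PSA rise".
- **Both definitions:** "Administration of salvage therapy (hormones, surgery, etc...) will be considered failure".
- **Analysis (11.1):** response rates with 95% confidence intervals and a one-sample Kaplan-Meier analysis at 5 years. The sample sizes are 32 for a PSA DFS of 80% (monotherapy) and 40 for 70% (boost), each with a total interval width of 0.30.

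No section says how the 60-month visit maps to the 5-year read-off.

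**The concern.** The endpoint and the visits run on different clocks, and enrollment always comes before the end of radiation. The visit that should close the 5-year assessment therefore usually falls after 5 years on the endpoint's clock. With no Phoenix backdating, failures found there miss the read-off. A response rate counted through the same visit would include them, so two outputs planned in 11.1 can disagree on the primary endpoint, with no rule for which one stands.

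The ASTRO problem is separate and does not depend on the time origin. After month 36 visits are yearly and stop at month 60, so a first rise at month 48 or 60 can never be followed by two more scheduled rises.

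Both effects make the result look better. The ASTRO label also matters for the HDR comparison: Section 1 says there are too few Phoenix results to project an HDR rate, so that comparison rests mainly on ASTRO.

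**Working it through.** **1. The plan's own figures.** Exact (Clopper-Pearson) 95% intervals have width 0.2985 at n = 32 and 80%, and 0.2997 at n = 40 and 70%. In both cases this is the smallest n with width at most 0.30, so 32 and 40 are reproduced and are not in dispute.

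**2. Lag from enrollment to last radiation.** Section 6.2 allows 90 days to the first radiosurgery fraction, and 8.4.4.1 gives a course of under 10 days, so at most about 99 days (3.3 months) for monotherapy. For boost, 8.1 puts IMRT after the boost while 11.1 puts it before. These passages must be reconciled; both orders are used here only to bound the lag. Assumed, because the documents do not say: earliest fraction about day 10, IMRT in 25 to 28 fractions.

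- Monotherapy: 15 to 99 days.
- Boost: 46 to 139 days (order in 8.1) or 46 to 99 days (order in 11.1).

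At 30.44 days per month, 15 days is 0.5 and 139 days is 4.6 months. The nominal 60-month visit therefore falls at about month 60.5 to 64.6 from enrollment.

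**3. Share of 60-month-visit Phoenix failures dated by month 60** (visits uniform over ±30 days): boost 0%. Monotherapy is 2-3% with the lag uniform over the allowed range, 13% if all lags are 15 to 30 days, and 25% if every lag is 15 days.

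**4. ASTRO runs on the schedule.**

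| First rise (month) | Third rise (month) | Failure date (months after radiation) |
|---|---|---|
| 6 | 18 | 4.5 |
| 12 | 24 | 9 |
| 18 | 30 | 15 |
| 24 | 36 | 21 |
| 30 | 48 | 27 |
| 36 | 60 | (30 + 36)/2 = 33 |
| 48 or 60 | not possible | none |

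Month 33 after radiation is about month 33 to 38 from enrollment.

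**5. Illustrative size.** Assume a constant hazard and ignore salvage and off-schedule PSA. If the true 5-year rate is S, the value read is S^((c + lag)/60), with c = 48 for Phoenix and 36 for ASTRO. Lag 0 is the case where the hazard runs on the radiation clock. Section 11.1 does not say which definition its rates refer to, so both are tried.

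| S | Phoenix reads | ASTRO reads |
|---|---|---|
| 0.80, lag 99 days to 0 | 82.6-83.7% | 86.4-87.5% |
| 0.70, lag 139 days to 0 | 73.2-75.2% | 78.6-80.7% |
| 0.70, lag 99 days | 73.7% | 79.2% |

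Example: 0.80^(48/60) = 0.837. At the rates predicted in Section 1 (lag 0), Phoenix and ASTRO read 91.9% and 93.9% for 90%, 87.8% and 90.7% for 85%, 83.7% and 87.5% for 80%, and 79.4% and 84.1% for 75%.

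In patients: 32 × 2.6-3.7% is about 1 missed Phoenix failure and 32 × 6.4-7.5% about 2 missed ASTRO failures. For boost, 40 × 3.2-5.2% is 1 to 2, and 40 × 8.6-10.7% is 3 to 4.

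**6. Coverage of the exact 95% interval for S.** This takes a binomial count with the read value as its probability.

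- Phoenix monotherapy 97.3-97.7%, against 97.6% without bias.
- Phoenix boost 90-94%, against 96%.
- ASTRO monotherapy 92-94%.
- ASTRO boost 67-78%, or 89-92% if salvage catches half the missed failures.

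**7. Simulated Kaplan-Meier, Phoenix** (6,000 trials per case, lags and visits uniform over their ranges, hazard on the radiation clock; bias in points, monotherapy / boost).

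- Read at month 60: +3.5 / +5.3.
- Read at window close using individual visit dates: -9.7 / -13.6, SD about 20. The estimate falls to 0 in 4% / 7% of trials, because censoring failure-free patients at their own visits empties the risk set.
- Read at window close with all 60-month results at one time: -0.1 / +0.1, SD 7, equal to the response rate through that visit.

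**The case against.** **Kaplan-Meier may not be meant for bDFS.** Section 11.1 names it for disease-free survival, which 9.4.3.2 defines separately, and the sample sizes are for a single proportion. A response rate through the last visit would count the Phoenix failures. This is a possible reading. But 11.1 sizes the study on 5-year PSA DFS and 9.4.1 defines bDFS as a time to PSA failure, so Kaplan-Meier is the natural reading. If both are reported, the disagreement between them remains.

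**The landmark is only unspecified.** No section requires reading at exactly month 60 from enrollment. True, but that is the plain result of a 5-year rate with an enrollment origin, and no other rule is given.

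**The lag is not documented.** This stands for monotherapy: with uniformly short lags, up to a quarter of these failures could be dated in time. It does not alter the boost result.

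**The effect is small or fragile.** For Phoenix monotherapy it is about one patient, and coverage hardly moves. The ASTRO sizes need a constant hazard and no salvage, and the recommended ADT could move failures either way. Both points stand as limits on size. The direction does not depend on them, and a larger sample would not remove the bias.

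**The HDR series may share the ASTRO limit.** Possibly. The documents do not show how those series dated failures, so the effect on the comparison cannot be sized.

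**Conclusion.** The concern holds and should be fixed. The ASTRO limit follows from the visit schedule alone. The Phoenix omission is effectively complete for boost and nearly complete for monotherapy, except for early-window visits with a lag under 30 days and failures caught before year 5 by salvage or off-schedule PSA.

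Measured against failure found through the scheduled year-5 visit, the upward bias at the planned rates is 2.6 to 3.7 (monotherapy) and 3.2 to 5.2 (boost) points for Phoenix, and 6.4 to 7.5 and 8.6 to 10.7 points for ASTRO. With IMRT before the boost, the boost low ends become 3.7 and 9.2. At 85-90% the bias is 1.9 to 2.8 points for Phoenix and 3.9 to 5.7 for ASTRO. These are upper values for a constant hazard; if salvage catches half of the missed failures, each one halves. Only ASTRO boost shows a marked loss of coverage.

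**What to change.** Keep the enrollment origin, which matches overall survival in 9.4.3.4, and keep both definitions as primary. Add to 9.4 and 11.1:

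1. A failure first found at the 60-month visit, within its ±30-day window, counts as a 5-year failure in both the Kaplan-Meier estimate and the response rate.
2. In the Kaplan-Meier estimate, enter every 60-month-visit result, failing or failure-free, at one stated common time at the close of that window, and read the estimate there. Do not censor failure-free patients at their own visit dates. The window closes at a different time for each patient on the enrollment clock, so the text must name one time; its exact value does not matter as long as all results share it.
3. Label the ASTRO figure, including in the HDR comparison, as capturing PSA failures with a first rise up to month 36 (dated to month 33 after radiation), not as a full 5-year rate.

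This is wording only: no new visits, no change of origin, and the sample sizes stay at 32 and 40. The Phoenix Kaplan-Meier rate will read about 3 to 5 points less favourable at the planned rates, or about 2 to 3 at 85-90%. Against a strict 60-month rate from enrollment (hazard on that clock), the corrected estimate reads about 0.5 / 1.2 points low, because the visit falls slightly later. The ASTRO limit is disclosed, not removed.
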